Written material	Extensive content available online. Limited content available as pamphlets and WhatsApps. No systematic distribution of WhatsApp messaging.	Printed copies of PACK Home Volume 1 (Be coronavirus safe) and Volume 2 (COVID-19 Caring at home).	Printed copies of PACK Home Volume 1 and 2. WhatsApp optimised versions of content delivered daily.
Community Health Worker visits	Mainly alongside chronic medication delivery.	Mainly alongside chronic medication delivery.	Additional one off household assessment to establish relationship at baseline.
Equipment	Distributed through drives.	Masks and hand sanitiser at enrolment.	Masks, hand sanitiser, bleach, gloves (to wear when using bleach). Plus on demand during follow-up.
Telephonic and text message support	On demand hotline service.	On demand hotline service	Scheduled support: Active phase (until 14 days after last person in household diagnosed): daily.

			Follow-up phase: 3 times a week for 7-14 days. Close-out: 5 days (to facilitate full integration into usual services).
--	--	--	---

* As of 06/07/2020 patients are considered at risk of severe COVID-19 if they are: 55 years or older or of any age with any one of the following: diabetes, on TB treatment, HIV, kidney disease, hypertension, previous TB, chronic lung disease, on cancer treatment.

Outcomes will be independently assessed by research staff who are also collecting biological samples at 0, 1, 2, 3, and 4 weeks. Baseline surveys will collect information on demographics, COVID-19 symptoms, household tracing information and home/ dwelling characteristics that impact transmission (size, rooms, ventilation, access to safe water, laundry facilities). Patient and household contact surveys will also include standardised measures to assess psychosocial functioning: General Health Questionnaire; UCLA Loneliness Scale and a version of the Brief AIDS-Related Stigma scale adapted for COVID-19. Research staff will complete a checklist documenting uptake of infection control measures at all follow-up contacts (1, 2, 3, 4 weeks). A sample size of 120 households (60 per group; 320 patient and household contacts per group) will provide 80-99% power to detect a 40% reduction in R₀ (2.5 to 1.5) varying the intra-cluster correlation efficient from 0.90 (80%) to 0.05 (99%) (Table 3). Index patients and their contacts will be reimbursed with R150 for their time at the baseline and final study visits.

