Overview

A cluster randomised controlled study with longitudinal follow up of SARS-CoV-2 infection in 120 households which have newly diagnosed positive cases. The index cases and their HHC will be invited and enrolled after informed consent. Baseline surveys and SARs-CoV-2 screening (PCR and IgM/IgG serology) and then weekly SARs-CoV-2 screening (PCR and serology) of HHC will occur at 0, 1, 2, 3 and 4 weeks. The households will be randomized to an intensified COVID19 infection mitigation intervention (n=60) administered by CHWs vs the standard messaging (n=60). Please see Figure 1 for a schematic overview of the study design.

EUC = enhanced usual care

Figure 1: Flow chart and schematic overview of the study design.

Sample Size Determination

We calculated the different effect sizes (Table 1). Based on exponential test for comparing hazards, assuming $120*6=720$ subjects, different intraclass correlation coefficients (ICCs) and comparing $R_0=2.5$ (with resulting incidence of 0.208 among 720 subjects) to a reduced R_0 of 0.9 (64% reduction, with resulting incidence of 0.075 among 720 subjects) or 1.25 (50% reduction) or 1.5 (40% reduction).

Table 1: ICC calculations

ICC	R0 2.5 to 0.9	R0 2.5 to 1.25	R0 2.5 to 1.5
	64% reduction	50% reduction	40% reduction
0.05	1.00000	1.00000	0.999944
0.25	1.00000	0.999891	0.991312
0.50	0.999993	0.995042	0.935880
0.75	0.999729	0.972942	0.846222
0.90	0.999033	0.951485	0.792745

Randomization and stratification

After completing consent, households will be randomised in a 1:1 ratio in blocks of 10 (60 households per group; 360 patient and household contacts per group).

Overview of data and data sources for analysis

All data are collected with two individual identifiers: study ID and PID (Western Cape Government health number). The exception is data source #4, which only uses PID.

1. Redcap database
 - a. Baseline survey of index patient and household characteristics (demographics, COVID-19 symptoms, household tracing information, home/dwelling characteristics that impact transmission (size, rooms, ventilation, access to safe water, laundry facilities))
 - b. Uptake of infection control measures at all follow-up contacts (assessment of use of isolation measures and cleaning of household surfaces up to 10 days post case of last diagnosis in household, at 1, 2, 3, 4 weeks).

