6. DEMOGRAPHICS AND BASELINE CHARACTERISTICS

6.1. Screening

The screening process will be described including presentation of numbers screened, numbers enrolled into the study and summary statistics on time between positive test of the index client and enrollment into the study.

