7. ANALYSIS OF PRIMARY STUDY OUTCOMES

7.1. The proportion of SARS-CoV-2 transmitted to HHC of the index COVID19 cases over a 4 week period

SARS-CoV-2 infection in a HHC will be defined as a positive PCR or evolving positive serologic test in a HHC who had a negative PCR or negative serology at baseline. The incidence of SARS-CoV-2 infection in HHC will be calculated as the number of new cases divided by the person time at risk and 95% confidence intervals calculated based on the Poisson distribution adjusted for clustering by household. This incidence as well as the timing to transmission will be analysed using exponential shared frailty models taking the clustering by household into account and allowing for censoring. The start time will be the date of diagnosis of the index case and the event time the date of diagnosis of the HHC using the date of the first positive test based on PCR or serology. Models will include possible confounders including adjustment for baseline values.

7.2. The proportion of transmissions to HHC in the enrolled households of index COVID cases assigned to the infection mitigation intervention arm compared with the households in the enhanced usual care (EUC) arm.

The incidence of SARS-CoV-2 will be estimated for the different study arms and incidence of and timing to SARS-CoV-2 per study arm will be compared by including study arm in the exponential frailty models.

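### The stated power is for a 40% fall in total R0 with every subject counted as an event; the arm comparison tests a post-baseline infection hazard, with no allowance for contacts already infected at week 0

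*SAP*

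**What the plan says.** SAP section 3 (Sample Size Determination, Table 1) and the protocol (Statistical Analysis and sample size, Table 3) give the same calculation. It is "Based on exponential test for comparing hazards", takes 120 households of 6, and compares a control R0 of 2.5, "with resulting incidence of 0.208 among 720 subjects", with 0.9 ("with resulting incidence of 0.075 among 720 subjects"), 1.25 or 1.5. For 2.5 to 1.5 the printed power runs from 0.999944 (ICC 0.05) to 0.792745 (ICC 0.90). The protocol's Approach section concludes that 120 households "will provide 80-99% power to detect a 40% reduction in" R0.

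The analysis is defined differently. SAP 7.1 counts a new infection "in a HHC who had a negative PCR or negative serology at baseline", starts the clock at the index case's diagnosis, and fits exponential shared frailty models with censoring. SAP 7.2 adds study arm to those models. Outcomes are assessed over 4 weeks.

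The plan foresees infection before week 0. Households enter after the index diagnosis and are randomised after consent. SAP 6.1 will summarise the "time between positive test of the index client and enrollment into the study". Contacts are tested at week 0, and secondary objective 3 describes exposure already present then.

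**The concern.** The power statement and the arm comparison refer to different quantities. The first concerns total R0 over all 720 subjects. The second concerns the hazard of new infection among contacts negative at baseline, most of whom would be censored uninfected at 4 weeks. Infections already present at week 0 cannot be prevented by STOPCOV. Excluding them reduces both the number at risk and the events; counting them adds cases to both arms that the intervention could not affect. Neither document allows for them.

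A null result would be read as coming from a trial with 80-99% power for a 40% reduction. The written analysis does not deliver that power for a 40% reduction in the hazard it estimates, and that hazard reduction is not a 40% reduction in R0.

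**Working it through.** **1. Reproduce the printed column (R0 2.5 to 1.5).** Inputs: 720 subjects, 6 per household, ratio 1.5/2.5 = 0.6. Alpha is not stated; two-sided 0.05 is inferred because it fits.

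Power = Φ[(1 − 0.6)·√(n/(1 + 0.6²)) − 1.96], with n = half of 720/(1 + 5·ICC).

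With effective totals of 576, 320, 206, 151 and 131, this returns the printed 0.999944, 0.991312, 0.935880, 0.846222 and 0.792745. The formula has no censoring: every subject is an event. Only the ratio and N matter, so the printed incidence plays no part.

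**2. The printed incidence.** 0.208 = 60 × 2.5/720 = 2.5/12, and 0.075 = 60 × 0.9/720. Each divides one arm's cases by both arms' subjects. A mean of 2.5 cases among 6 contacts is 2.5/6 = 0.417, the figure used below.

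**3. Event-based power for a post-baseline hazard ratio of 0.6.** Let f be the assumed share of the 2.5 cases present at baseline.

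- Infected at baseline: p = 2.5f/6
- At risk per household: m = 6(1 − p)
- Control risk: q1 = [2.5(1 − f)/6]/(1 − p)
- Intervention risk: q2 = 1 − (1 − q1)^0.6
- Events per arm: D1 = 60·m·q1, D2 = 60·m·q2
- Design effect: DE = 1 + (m − 1)·ICC
- Power = Φ[0.511/√(DE/D1 + DE/D2) − 1.96], where 0.511 = |ln 0.6|

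Example, f = 30%, ICC 0.05: p = 0.125, m = 5.25, q1 = 0.333, q2 = 0.216, D1 = 105, D2 = 68, DE = 1.2125. The standard error is 0.171 and power is 85%.

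| ICC | Printed | f = 0 | 10% | 30% | 50% |
|---|---|---|---|---|---|
| 0.05 | 99.99% | 94% | 92% | 85% | 72% |
| 0.25 | 99.1% | 75% | 72% | 63% | 51% |
| 0.50 | 93.6% | 56% | 53% | 46% | 37% |
| 0.90 | 79.3% | 39% | 37% | 32% | 26% |
| Events | 720 | 249 | 224 | 173 | 123 |

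The step from the printed column to f = 0 is the event-count fault. The steps to the right are the loss from baseline infection: 2-4, 7-12 and 13-24 points. A simulation with beta-binomial households and a cluster-robust log hazard ratio (4,000 trials per cell) agrees within about two points.

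**4. A plausible range for f.** Under the SAP's constant-hazard model with its clock at index diagnosis, λ = −ln(1 − 0.417)/28 = 0.01925 per day and f(d) = (1 − e^(−λd))/0.417. A delay to baseline of 2, 4 or 7 days gives 9%, 18% or 30%. Infection before the index diagnosis would add to this, by an amount the documents do not allow one to calculate.

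**5. The effect in R0 terms.** A hazard ratio of 0.6 after baseline gives total R0 = 2.5f + m·q2, that is 1.66, 1.73, 1.88 or 2.05 at f = 0, 10, 30 or 50%. Conversely, a total R0 of 1.5 needs post-baseline cases to fall by 1/[2.5(1 − f)]: 40% at f = 0, then 44%, 57% or 80%.

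**The case against.** The strongest objection is that the documents name the effect as R0 2.5 to 1.5, and step 3 tests something else. It stands. A reader might infer that baseline infections make the power claim for that R0 effect too high even at the lowest ICC. The calculation does not support this. If intervention-arm post-baseline cases are set at 1.5 − 2.5f, event-based power at ICC 0.05 is 98.8% at f = 0, 99.3% at 10% and 99.9% at 30%. At ICC 0.90 it is 52%, 57% and 70%. Power rises with f because the required post-baseline effect grows. Whether falls of 57% or 80% are plausible is a separate question about the effect size. The 52% at ICC 0.90 is still short of the printed 79.3%, but at f = 0 baseline infection plays no part in that shortfall.

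A second objection, also right, is that most of the distance from the printed values is the event-count fault. Within the table's own uncensored method, removing the infected contacts at f = 50% moves power only from 99.99% to 99.96% (ICC 0.05) and from 79.3% to 79.1% (ICC 0.90). That method is not the planned censored analysis, but the two faults must be reported separately.

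Third, the quoted 0.208 might be read as showing that all 2.5 cases per index were entered as events. It does not: it is half of 2.5/6 and has no influence on the table.

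Fourth, f is assumed, and the 50% column goes beyond what a 7-day delay implies.

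Finally, one cannot say flatly that baseline infections will be excluded. The 'or' in SAP 7.1 admits a contact who is PCR-positive but antibody-negative at baseline. If such cases were counted in both arms, the effect would be diluted: at f = 30% a risk ratio of 0.6 becomes 0.3 + 0.7 × 0.6 = 0.72.

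**Conclusion.** The mismatch is real, and the power statement should be redone. For a 40% reduction in the hazard that SAP 7.2 estimates, power is about 94% to 39% across ICC 0.05 to 0.90 before any baseline exclusion, not 99.99% to 79.3%; the event-count fault accounts for that gap. Baseline infection takes a further 2-4 points at f = 10%, 7-12 at 30% and 13-24 at 50%, for the same post-baseline hazard ratio only. In addition, the effect is misnamed: even at f = 0 a 40% hazard cut corresponds to R0 of about 1.66, not 1.5.

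These figures assume 6 contacts in each of 120 households, 0.417 as the 4-week control risk, two-sided 0.05, no dropout, and exclusion of contacts infected at baseline. If the printed 0.208 really were the per-contact risk, power for 0.208 versus 0.125 with 360 per arm (two proportions, no baseline exclusion) would be 77% at ICC 0.05 and 25% at ICC 0.90.

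**What to change.** Keep 120 households. In the protocol (the Approach power sentence and Table 3) and SAP section 3 (Table 1):

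- Recompute power from expected post-baseline events among contacts at risk at baseline, with censoring at 4 weeks.
- Give rows for assumed baseline-infected shares, for example 0, 10, 30 and 50%, or use pooled, arm-blinded baseline positivity if it is available.
- State alpha and sidedness, and reconcile 0.208 (2.5/12) with 2.5 cases among 6 contacts (0.417).
- Name the effect as the post-baseline infection hazard ratio, and give the total-R0 change it corresponds to.

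In SAP 7.1, require contacts to be negative on both PCR and serology at baseline, so that the analysed population matches the one used for sizing.

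The cost is rewording and a new table, with no extra participants, visits or tests. The drawback is that the stated power becomes less favourable.

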4. STUDY OUTCOMES

4.1. Primary study outcomes

- The incidence rate of SARS-CoV-2 infections among HHC of the index COVID19 cases over a 4 week period
- The time to transmission to HHC during that time period
- The association between the time to transmission and clinical symptoms of the index cases
- The symptomatic/asymptomatic ratio among transmitted SARS-CoV-2 in household contacts
- The proportion of transmissions to HHC in the enrolled households of COVID cases assigned to the infection mitigation intervention arm compared with the households in the enhanced usual care (EUC) arm.

4.2. Secondary Outcomes

- The proportion of index patients and HHC that visited a primary health clinic during the period of follow-up in the intervention arm as compared to the enhanced usual care (EUC) arm.
- The proportion of index patients and HHC that were hospitalised for COVID-19 during the period of follow-up in the intervention arm as compared to the enhanced usual care (EUC) arm.
- The proportion of index patients and HHC that died due to COVID-19 during the period of follow-up in the intervention arm as compared to the enhanced usual care (EUC) arm.
- The proportion of index patients and HHC that showed improved psychosocial functioning, defined as lower GHQ 12, UCL loneliness scores and Stigma scores, in the intervention arm as compared to the enhanced usual care (EUC) arm.
- The proportion of SARS-CoV-2 transmitted to HHC of the index COVID19 cases over a 4 week period, stratified by COVID-19 wave.
- The proportion of index patients and HHCs who developed antibodies during follow-up.
- Process Evaluation Outcomes:
 - Barriers and facilitators to implementation of the STOPCov intervention.
 - Identified contextual patterns within households that interact with the implementation of STOPCov intervention
 - Theoretical explanations of how different structural relations and mechanisms impact on intervention delivery and outcomes.
 - Generalizable inferences and predictions on how best to optimise the STOPCov intervention.

5. GENERAL PRINCIPLES OF ANALYSIS

The statistical analysis plan will be finalised and signed-off prior to database lock. Post-hoc analysis (analyses performed that are different from those described in the final version of the SAP) will be documented in the final report.

Descriptive summaries will be presented using summary statistics (e.g. number (n), mean, standard deviations (SD), median, minimum, maximum) and 95% confidence intervals (CI) for continuous parameters or frequency distributions (n, %) for categorical parameters.

In general, all households who entered the study will be included in the statistical evaluation (intention-to-treat analysis). Households who completed the final screening will be included in the per-protocol analysis. There will be no predefined interim statistical analysis or stopping rules.

All output will be generated using STATA SE Version 13 or R. No missing data will be replaced, and it will be shown in any summaries as missing.

6. DEMOGRAPHICS AND BASELINE CHARACTERISTICS

6.1. Screening

The screening process will be described including presentation of numbers screened, numbers enrolled into the study and summary statistics on time between positive test of the index client and enrollment into the study.

6.2. Study Completion

The data on completion of the study and reasons for withdrawal will be summarized. The number of households or participants withdrawing and the reason for withdrawal will also be reported and summarized by time in the study.

6.3. Demography and Baseline Characteristics

Demographic data and baseline characteristics of index clients, households and household contacts will be summarized. Summary statistics will be adjusted for clustering by household.

6.4. Compliance

Uptake of the intervention will be described, including over time.

6.5. Protocol Deviations

All protocol deviations will be reported.

7. ANALYSIS OF PRIMARY STUDY OUTCOMES

7.1. The proportion of SARS-CoV-2 transmitted to HHC of the index COVID19 cases over a 4 week period

SARS-CoV-2 infection in a HHC will be defined as a positive PCR or evolving positive serologic test in a HHC who had a negative PCR or negative serology at baseline. The incidence of SARS-CoV-2 infection in HHC will be calculated as the number of new cases divided by the person time at risk and 95% confidence intervals calculated based on the Poisson distribution adjusted for clustering by household. This incidence as well as the timing to transmission will be analysed using exponential shared frailty models taking the clustering by household into account and allowing for censoring. The start time will be the date of diagnosis of the index case and the event time the date of diagnosis of the HHC using the date of the first positive test based on PCR or serology. Models will include possible confounders including adjustment for baseline values.

7.2. The proportion of transmissions to HHC in the enrolled households of index COVID cases assigned to the infection mitigation intervention arm compared with the households in the enhanced usual care (EUC) arm.

The incidence of SARS-CoV-2 will be estimated for the different study arms and incidence of and timing to SARS-CoV-2 per study arm will be compared by including study arm in the exponential frailty models.

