Household Contacts (HHC)						
	ICF		x			
	Demography survey		x			
	Symptom check	x		x	x	x
	COVID19 PCR	x		x	x	x
	COVID serology	x		x	x	x
	Follow up surveys	x		x		x

Data Collection and Management: Data will be collected by study staff on handheld devices. Data will be downloaded daily to a central database housed at the DTHF head office. Further details are available in Work Package 5 and the Data Management document.

Statistical Analysis and sample size: We will describe and compare the characteristics and survey outcomes, isolation, and linkages of participants. We calculated the different effect sizes (Table 2). Based on exponential test for comparing hazards, assuming $120*6=720$ subjects, different intraclass correlation coefficients (ICCs) and comparing $R_0=2.5$ (with resulting incidence of 0.208 among 720 subjects) to a reduced R_0 of 0.9 (64% reduction, with resulting incidence of 0.075 among 720 subjects) or 1.25 (50% reduction) or 1.5 (40% reduction).

Table 3: ICC calculations

ICC	Ro 2.5 to 0.9	Ro 2.5 to 1.25	Ro 2.5 to 1.5
	64% reduction	50% reduction	40% reduction
0.05	1.00000	1.00000	0.999944
0.25	1.00000	0.999891	0.991312
0.50	0.999993	0.995042	0.935880
0.75	0.999729	0.972942	0.846222
0.90	0.999033	0.951485	0.792745

The analyses will be determined by the study analysis plan. These analyses include the calculation of the proportion of SARS-CoV-2 positive individuals screened over a 3-month period, the transmissibility of the virus by determining the proportion of SARS-CoV-2 transmitted to household contacts of the identified COVID19 cases over a 4-week period, the period of infectiousness by correlating the time to transmission and clinical symptoms of the index cases, and the symptomatic/asymptomatic ratio among transmitted SARS-CoV-2 in household contacts. The Ro will be determined by both looking at new cases among the population in contact with the index cases and the total population (both in our service and other clinics in the area) diagnosed over time. The main outcome relates to the incidence of new cases of COVID19. These will be analysed using mixed effect Poisson regression models and frailty models to take the clustering by household into account. Both these regression models take the duration of follow up into account. Scores (e.g., GHQ) will be baseline adjusted. Qualitative data will be transcribed, translated and inductively analysed for themes.

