8.3. The proportion of index patients and HHC that showed improved psychosocial functioning in the intervention arm as compared to the enhanced usual care (EUC) arm. 10	
8.4. The association between the time to transmission and clinical symptoms of the index cases.....	10
8.5. The symptomatic/asymptomatic ratio among transmitted SARS-CoV-2 in household contacts	10
8.6. The incidence of SARS-CoV-2 transmitted to HHC of the index COVID19 cases over a 4 week period, stratified by COVID-19 wave.....	10
8.7. Analysis of household exposure to SARS-CoV-2 at baseline using the baseline serology result, and development of antibodies using the serology result during follow-up. 10	
8.8. Process Evaluation Analysis.....	11

1. ***INTRODUCTION***

This Statistical Analysis Plan (SAP) describes the statistical methods to be used during the analysis and reporting of data collected for the TRACE study. This SAP should be read in conjunction with the Study Protocol (dated 15 December 2020), Case Report Forms (CRFs, Final Versions, dated 4 November 2020) and Data Management Plan (DMP, dated 18 June 2020).

2. ***OBJECTIVES OF THE STUDY***

2.1. **Primary objectives**

1. To measure frequency and timing of transmission of SARS-CoV-2 to household contacts.
2. To investigate the effect of an intensive infection mitigation intervention (STOPCOV) administered by lay health care workers on the household transmission of SARS-CoV-2.

[figure not shown]
2.2. **Secondary objectives**

1. To investigate the effect of the STOPCOV intervention on clinical outcomes and psychosocial functioning
2. To investigate the difference in transmission of SARS-CoV-2 to HHC stratified by COVID-19 wave (first or second wave)
3. To describe the household exposure to SARS-CoV-2 at baseline using the baseline serology result, and development of antibodies using the serology result during follow-up.
4. To assess acceptability, feasibility and contextual factors impacting intervention delivery (process evaluation), specifically:
 - a. To understand the acceptability and feasibility of the STOPCov intervention.
 - b. To understand how context shapes implementation of the STOPCov intervention at the level of households and individuals.
 - c. To provide explanations for observed trends in the trial findings.
 - d. To generate theoretical generalisations of how to optimise wider implementation of the STOPCov intervention to other households to reduce transmission of COVID-19.

3. ***DESIGN OF THE STUDY***

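### One baseline rule in SAP 7.1 serves both the Aim 1 description and the arm comparison, and neither way of reading its *or* suits both

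*SAP*

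**What the plan says.** The first primary objective (SAP 2.1) is "To measure frequency and timing of transmission of SARS-CoV-2 to household contacts". SAP 7.1 answers it with a single case rule: a positive PCR, or an evolving positive serology, "in a HHC who had a negative PCR or negative serology at baseline". The incidence is the "number of new cases divided by the person time at risk". For the frailty model, "The start time will be the date of diagnosis of the index case and the event time the date of diagnosis of the HHC", taken as the first positive PCR or serology.

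SAP 7.2 has no case rule or risk set of its own. The arms are compared "by including study arm in the exponential frailty models", that is, in the models of 7.1.

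Index diagnosis precedes enrolment. SAP 6.1 will report "summary statistics on time between positive test of the index client and enrollment into the study", but the documents give no expected length for that delay. Contacts have PCR and serology at baseline and at weeks 1 to 4 (SAP, overview of data sources). SAP 8.7 uses the baseline serology in a secondary description. No analysis counts baseline PCR positives as prevalent infections.

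**The concern.** The two aims need different sets of contacts. An infection already present at the baseline visit cannot be an effect of STOPCOV, so it should not be an event in the arm comparison. The same infection may well be a household transmission, and an early one, so it belongs in a description of how often and when transmission occurs.

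One rule cannot do both, and the *or* leaves open which aim is served badly. At stake are the frequency and timing results for Aim 1, the symptomatic ratio in SAP 8.5 (which covers the same transmitted infections) and, on the literal reading, the randomised comparison itself.

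**Working it through.** **Step 1: the rule applied to each baseline result.**

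| Baseline PCR / serology | Literal *or* | Read as both negative |
|---|---|---|
| negative / negative | in | in |
| positive / negative | in | out |
| negative / positive | in | out |
| positive / positive | out | out |

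Read literally, a PCR-positive, seronegative contact is a case dated at the baseline visit. If *new* is taken to require a later test, the same contact still qualifies through a further positive PCR or seroconversion. A PCR-negative, seropositive contact counts only with a later positive PCR or an evolving serology, a term left undefined. Because 7.2 uses the 7.1 models, each row applies to both aims.

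**Step 2: the plan's own figure.** The sample-size text gives an incidence of 0.208 for R0 = 2.5. This is 60 × 2.5 / 720 = 150/720 = 0.208: one arm's cases over both arms' subjects. Per household of 6 contacts, 2.5 transmissions are 2.5/6 = 0.417. The documents do not print 0.417; it is the reference used below.

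**Step 3: Aim 1, both-negative reading.** Let f be the share of the 2.5 transmissions already positive at baseline (assumed, all caused by the index). The count kept is 2.5(1 − f). The at-risk share is 2.5(1 − f)/(6 − 2.5f).

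- f = 20%: 2.0/5.5 = 0.36
- f = 40%: 1.5/5.0 = 0.30
- f = 60%: 1.0/4.5 = 0.22

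Starting instead from the printed 0.208 (1.25 per 6 contacts), the same f values give 1.0/5.75 = 0.174, 0.75/5.5 = 0.136 and 0.5/5.25 = 0.095.

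**Step 4: Aim 1, literal reading.** Only double positives are lost. Let d be their share of baseline positives (assumed 10% or 50%), and let all single positives count. The at-risk share is 2.5(1 − fd)/(6 − 2.5fd).

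- f = 20%: 2.45/5.95 = 0.412 (d = 10%); 2.25/5.75 = 0.391 (d = 50%)
- f = 40%: 2.40/5.90 = 0.407; 2.00/5.50 = 0.364
- f = 60%: 2.35/5.85 = 0.402; 1.75/5.25 = 0.333

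**Step 5: person-time, both-negative reading.** Let g be the days from index diagnosis to baseline (assumed). A contact who must be negative at baseline adds g days in which no event can be recorded. With 28 days of follow-up, the rate is multiplied by about 28/(28 + g): 28/30 = 0.93 for g = 2 and 28/35 = 0.80 for g = 7. The reported rate therefore moves with enrolment speed.

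**Step 6: arm comparison, literal reading.** Single positives number 2.5f(1 − d) per household in either arm. Suppose STOPCOV halves post-baseline transmission (50% is one of the plan's own effect sizes), with d = 10% and all single positives counted as cases.

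- f = 20%: 0.45 + 2.0 = 2.45 against 0.45 + 1.0 = 1.45, a 41% reduction
- f = 40%: 0.90 + 1.5 = 2.40 against 0.90 + 0.75 = 1.65, a 31% reduction
- f = 60%: 1.35 + 1.0 = 2.35 against 1.35 + 0.5 = 1.85, a 21% reduction

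These show the direction and rest wholly on assumed f and d.

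**The case against.** The strongest reply is that the rule says *or*. A reader might infer that every contact infected by the baseline visit is excluded, so that the earliest transmissions vanish from Aim 1 and the arm comparison is protected. The documents do not support that. On the written rule only double positives are barred, and a PCR-positive, seronegative contact, plausibly the most recent infection, is retained in both analyses. This limits the Aim 1 loss, but it also means the arm comparison is not protected.

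A reader might also infer that R0 must be understated. That goes too far. The protocol says "The Ro will be determined by both looking at new cases among the population in contact with the index cases and the total population" diagnosed over time, and the second source does not depend on the 7.1 rule. SAP sections 7 and 8 set out no R0 method, so any effect on R0 is indirect.

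An incidence estimand is legitimate: the protocol summary states Aim 1 as incidence and timing, and SAP 4.1 lists an incidence rate. But the SAP starts its clock at index diagnosis, so infections between then and the baseline visit lie on its own time axis. SAP 6.1 and 8.7 show part of the picture without feeding frequency or timing. Adjustment for baseline values, mentioned in 7.1, does not define who is at risk.

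Finally, not every baseline positive was infected by the index. Some may be co-primary cases, the index's own source, infected elsewhere, or past infections. This stands, and it is why a combined figure needs a caveat.

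**Conclusion.** The point holds in this form: 7.1 and 7.2 share one rule, and neither reading serves both aims. The literal reading loses double positives from Aim 1 and admits infections that predate the intervention to the arm comparison. The both-negative reading suits the arm comparison but removes all baseline positives from Aim 1 frequency and timing and makes the rate depend on enrolment delay.

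The direction for Aim 1 is understatement to the extent that baseline positives are household transmissions. The size is unknown because the documents give no baseline positivity. The range 0.36 to 0.22 against 0.417 assumes f of 20% to 60%, 6 contacts, infection by the index and the both-negative reading; under the literal reading the same f gives 0.412 to 0.333. The plan should be changed, because the ambiguity sits in the primary case definition.

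**What to change.** **SAP 7.2.** State that the arm comparison uses contacts negative on both PCR and serology at baseline, with time at risk from randomisation or from the baseline visit (name which).

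**SAP 7.1, Aim 1.** Replace the *or* rule with two reported components: baseline-prevalent infections (PCR-positive at baseline) and incident infections. Give each separately, and both combined over all tested contacts. In a timing sensitivity analysis, treat baseline positives as infected by the baseline visit: left-censored, with infection before index diagnosis allowed.

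**SAP 8.5.** Report the symptomatic ratio with and without baseline positives.

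**Interpretation.** Do not label the figures lower and upper bounds. State that baseline positives may include co-primary cases, the index's own source or infections acquired elsewhere; that later cases may be community-acquired; and that symptoms resolved before enrolment may be missed.

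**Cost.** No new visits or samples, since baseline PCR and serology are already collected. It needs SAP wording and a little more analysis; the left-censored model needs its own likelihood and time origin. The combined figure may overstate transmission from the index.
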